## List of Abbreviations and Definition of Terms

Abbreviation	Definition
ADA	Antidrug antibody
AE	Adverse event
ANCOVA	Analysis of covariance
CM	Chronic migraine
CMH	Cochran-Mantel-Haenszel
ECG	Electrocardiogram
EM	Episodic migraine
EOT	End of Treatment
ePRO	Electronic patient-reported outcome
EQ-5D-5L	EuroQol-5 Dimension, 5 response level version
ES	Enrolled Set
FAS	Full Analysis Set
HIT-6	6-Item Headache Impact Test
IMP	Investigational medicinal product
IRT	Interactive response technology
LS mean	Least Square Mean
MedDRA	Medical Dictionary for Regulatory Activities
MMRM	Mixed-effects model for repeated measures
MSQOL	Migraine-Specific Quality of Life
PCS	Potentially Clinically Significant
PGIC	Patient Global Impression of Change
PHQ-2	2-Item Patient Health Questionnaire
PHQ-9	9-Item Patient Health Questionnaire
PT	Preferred Term
RS	Randomized Set
SAP	Statistical Analysis Plan
SC	Subcutaneous
SD	Standard deviation
SE	Standard error
SMQ	Standardized MedDRA Queries
SOC	System Organ Class
SS	Safety Set
TEAE	Treatment-emergent adverse event
WPAI	Work Productivity and Activity Impairment

## 1 Introduction

This statistical analysis plan (SAP) documents the statistical methodology and data analysis algorithms and conventions to be applied for statistical analysis and reporting of efficacy, safety and pharmacokinetic data of Trial 406-102-00001. Analysis of immunogenicity is described in the bioanalytical protocol. All amendments to the protocol are taken into consideration in developing the SAP.

## 2 Trial Objectives

To evaluate the efficacy and safety of subcutaneous (SC) administration of TEV-48125 (monthly TEV-48125 225 mg [loading dose only: 675 mg] and TEV-48125 675 mg once over a period of 3 months) compared with placebo for preventive treatment in chronic migraine (CM) patients.

## 3 Trial Design

### 3.1 Type/Design of Trial

This is a multicenter, randomized, double-blind, placebo-controlled, parallel-group trial in CM patients. The schematic of the trial design is shown in [Figure 3.1-1](#).

The trial consists of a 4-week screening period and a 12-week double-blind treatment period.

After obtaining written informed consent from patients, the investigator will screen them for eligibility (Visit [V] 1/Screening). Subjects who have been diagnosed with CM, and who meet all the inclusion criteria and do not fall under any of the exclusion criteria will be randomized in a 1:1:1 ratio to one of the following 3 treatment groups (V2/Baseline). The investigational medicinal product (IMP) will be administered at V2/Baseline, V3/Month 1, and V4/Month 2 as specified in the protocol Section 3.2, Trial Treatments. Subjects will also visit the trial site at 3 to 10 days and at 14 to 21 days (twice) after one of IMP administrations at either V2/Baseline, V3/Month 1, or V4/Month 2 for pharmacokinetic assessment. Subjects will also return to the trial site (V5/End of treatment) for the final assessment at 12 weeks after the first IMP administration. Subjects who are withdrawn from the trial will undergo a withdrawal assessment.

The trial includes the following treatment groups.

- TEV-48125 675/225/225 mg group

[figure not shown]
- TEV-48125 675 mg/placebo/placebo group
- Placebo group

The period of trial participation for each subject is defined as the period from the day that informed consent is obtained from the patient until the day of trial completion.

Definition of the end of trial date for individual subject:

The end of trial date for individual subject is defined as the date of V5/End of treatment for the final assessment/observation or the date of trial withdrawal. The date of trial withdrawal is defined as the date of withdrawal assessment, the date of the final assessment/observation in the double-blind treatment period, or the date of withdrawal decision, whichever comes later. For subjects who are lost to follow up, the end of trial date for individual subject is defined as the date of their last visit/contact or the date of the last attempt to contact them.

Following the end of treatment visit (V5/End of treatment), subjects will be offered the opportunity to enter a long-term trial for the purpose of evaluating antidrug antibody (ADA) at 225 days (approximate equivalent of 5 half-lives) after the final dose of IMP (V4/Month 2) in this trial.

**Figure 3.1-1 Trial Design Schematic**

PBO = placebo; R = randomization.

**3.2 Trial Treatments**

In the trial, TEV-48125 or placebo will be subcutaneously administered once monthly for 3 months for a total of 3 doses. Monthly dosing refers to dosing every 4 weeks (acceptable window: ± 3 days). Subjects who visit the trial site earlier than the acceptable window will not receive the IMP and will be requested to return to the trial site within the acceptable window. The IMP will be administered by trial personnel responsible for administration of injections.

The dosing regimens for treatment groups are shown below.

- TEV-48125 675/225/225 mg group:  
Subjects will receive 675 mg of TEV-48125 as 3 active injections (225 mg/1.5 mL) at V2/Baseline and 225 mg of TEV-48125 as a single active injection (225 mg/1.5 mL) at V3/Month 1 and V4/Month 2.
- TEV-48125 675 mg/placebo/placebo group:  
Subjects will receive 675 mg of TEV-48125 as 3 active injections (225 mg/1.5 mL) at V2/Baseline and placebo as a single 1.5-mL injection at V3/Month 1 and V4/Month 2.
- Placebo group:  
Subjects will receive three 1.5-mg placebo injections at V2/Baseline and a single 1.5-mL placebo injection at V3/Month 1 and V4/Month 2.

At the time of each visit, the interactive response technology (IRT) will be queried and trial personnel will retrieve and administer a 1.5-mL volume from each syringe contained in the appropriately numbered kit(s).

Recommended SC injection sites follow the National Institutes of Health clinical center patient education materials: Giving a subcutaneous injection. The suggested sites of injection are the outside of upper arms, back of upper arms, abdomen, or front of thighs. At each visit and when 3 injections are administered at a visit, each of the injections should be given in a different location (eg, not in precisely the same place). Trial personnel responsible for administration of injections should inspect previous injection sites to ensure that they are free from bruising and tenderness and that proper rotation of sites is performed.

IMP should be removed from the refrigerator and allowed to equilibrate at room temperature for 45 to 60 minutes before IMP administration.

The date and time of SC injections and their locations will be recorded for each dosing visit (V2/Baseline, V3/Month 1, and V4/Month 2).

### **3.3 Trial Population**

#### **3.3.1 Number of Subjects and Description of Population**

A total of 540 male or female (180 per group, a total of 3 groups) with CM aged 18 to 70 years, inclusive, will be enrolled in the trial. The plan is to enroll at least approximately half of the subjects in Japan. The enrollment procedure will be continued until the number of enrolled subjects reaches 540.

Continued concomitant use of some preventive migraine medications (Table 4.1.2-1 in the protocol) may be permitted, so long as a stable dose and regimen have been maintained for at least 2 consecutive months prior to informed consent, in which case the subject will be allowed to continue using no more than 1 preventive medication. However, the total number of subjects receiving concomitant preventive medication during the trial will not exceed 30% of the total sample size of the trial.

## **4 Sample Size**

In a phase 2b trial in CM patients (Trial LBR-101-021), concerning the mean change from baseline in the monthly average number of headache days of at least moderate severity during the 12-week period after the first dose of IMP, the difference between the TEV-48125 675/225/225 mg group and the placebo group was 1.7 days and the standard deviation was 4.9 days. On the assumption that this trial will also yield a similar result to the phase 2b trial (Trial LBR-101-021), a sample size of 176 subjects per group gives more than 90% power for the trial to succeed at a significance level of 0.05 (two-sided). Based on the above and taking into account a small percentage of subjects who may be excluded from the FAS, the target sample size was determined to be 180 subjects per group and 540 subjects as the overall total included in the trial.

## **5 Statistical Analysis Datasets**

### **5.1 Analysis Sets**

- Enrolled set (ES):  
Subjects from whom informed consent has been obtained (including screen failures)
- Randomized set (RS):  
Randomized subjects in the ES
- Safety set (SS):  
Subjects in the RS who receive the IMP at least once
- Full Analysis set (FAS):  
Subjects in the SS who have at least 10 days of baseline and post baseline efficacy assessment data on monthly average number of headache days of at least moderate severity
- Pharmacokinetic Analysis set:  
The pharmacokinetic analysis set will include all subjects in whom at least 1 dose of TEV-48125 is administered, and date and time of blood sampling for plasma drug concentration is recorded for at least 1 time point after TEV-48125 dosing.

- Immunogenicity Analysis set:  
The immunogenicity analysis set will include all subjects in whom at least 1 dose of TEV-48125 is administered, and date and time of blood sampling for serum ADA assessment is recorded for at least 1 time point after TEV-48125 dosing.

For all analysis sets except for ES, treatment will be assigned based on the treatment to which subjects are randomized regardless of which treatment they actually received.

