## **8 Efficacy Analysis**

The FAS will be used for all efficacy analyses. Summaries will be presented by treatment group, unless otherwise noted. Descriptive statistics for all efficacy data will be presented by month (or week) and overall for the 12-week period. Descriptive statistics will include number of subjects, mean, SD, median, minimum, and maximum.

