### 8.1.2.2 Analysis With Multiple Imputation Method

Regarding the primary endpoint, when the monthly average number of headache days of at least moderate severity during the 12-week period after the first dose of IMP is not missing, but any of the monthly number of headache days of at least moderate severity during the 4-week period after each dose of IMP (ie, Month 1, Month 2, and Month 3) is missing, the multiple imputation (MI) method will be applied to impute the missing data for Month 1, Month 2, or Month 3 and the primary endpoint will be calculated as the average of Month 1, Month 2, and Month 3. The data will be processed by the following steps.

- If a subject has partial electronic headache diary data for a month, ie, <10 days of data, a value for that month will be considered missing before the MI procedure.
- Subjects in each TEV-48125 group who are withdrawn early for reasons of adverse events (AEs) or lack of efficacy will be assigned to the placebo group and their missing values will be imputed using data from the placebo-treated subjects.
- The SAS MI procedure will be run to create 100 complete datasets.
- Within each imputed data set, for a subject who has partial, eg, X days ( $X < 10$ ), electronic headache diary data for a month, the monthly value will be replaced by 
$$\sum (\text{observed days of at least moderate severity}) + (28 - X) * \text{imputed value} / 28$$
- The monthly average number of headache days of at least moderate severity during the 12-week period after the first dose of IMP will be the average of the Month 1, Month 2, and Month 3 values.

Each dataset including the monthly average during the 12-week period will be analyzed using the same ANCOVA model as described in [Section 8.1.1](#). The LS means and standard errors (SE) from each analysis will be output to a SAS data set. The SAS MIANALYZE procedure will be used to generate the final LS means ( $\pm$  SE) for the treatment groups and the treatment differences (each TEV-48125 group – placebo group) as well as the p-values associated with treatment differences. The 95% confidence intervals for the treatment differences will also be constructed.

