#### 8.1.4 Technical Computational Details for Primary Analysis

- Definition of headache day of at least moderate severity  
A headache day of at least moderate severity is defined as when at least one of the following situations occurs:
  - A calendar day (0000 to 2359) with headache pain that lasts  $\geq 4$  hours with a peak severity of at least moderate severity
  - A calendar day (0000 to 2359) when the subject used acute migraine-specific medication (triptans or ergots) to treat a headache of any severity or duration
- Variable definitions

The change from baseline in the monthly average number of headache days of at least moderate severity during the 12-week period after the first dose of IMP will be derived using the electronic headache diary data collected for the corresponding headache diary questions. The baseline value will be calculated using all data collected from the day of V1/Screening through the day before V2/Baseline and normalized to 28 days (ie, if the number of days from V1/Screening through the day before V2/Baseline is greater or less than 28 days, the baseline value will be normalized to 28 days; see the following formula).

$$\frac{\sum \text{Days of efficacy variable during the screening period}}{\sum \text{Days with assessments recorded in the eDiary for the screening period}} \times 28$$

The monthly average number of headache days of at least moderate severity during the 12-week period after the first dose of IMP will be derived and normalized to 28 days (see the following formula), if a subject has  $\geq 10$  days of electronic headache diary data after the first dose of IMP.

$$\frac{\sum \text{Days of efficacy variable over the 12 week period}}{\sum \text{Days with assessments recorded in the eDiary for the 12 week period}} \times 28$$

The monthly number of headache days of at least moderate severity during the 4-week period after each dose (ie, for Month 1, Month 2, and Month 3), will be

derived and normalized to 28 days (see the following formula), where monthly data separated by each visit for IMP dosing will be used. If a subject is withdrawn early or has intermittent missing days and has <10 days of electronic headache diary entries for a month, that month's value will be considered as missing.

$$\frac{\sum \text{Days of efficacy variable during the 4 week period}}{\sum \text{Days with assessments recorded in the eDiary for the 4 week period}} \times 28$$

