## 8.2 Secondary Endpoint

### 8.2.1 Secondary Analysis

The secondary endpoints in this trial are as follows:

- 1) Mean change from baseline in the monthly average number of migraine days during the 12-week period after the first dose of IMP
- 2) Proportion of subjects reaching at least 50% reduction in the monthly average number of headache days of at least moderate severity during the 12-week period after the first dose of IMP
- 3) Mean change from baseline in the monthly average number of days with use of any acute headache medications during the 12-week period after the first dose of IMP
- 4) Mean change from baseline in the monthly average number of headache days of at least moderate severity during the 12-week period after the first dose of IMP in subjects not receiving concomitant preventive migraine medications
- 5) Mean change from baseline in disability score, as measured by the HIT-6, at 4 weeks after the final (third) dose of IMP

For the endpoint 1), 3) and 4), will be analyzed using an ANCOVA model, Wilcoxon rank-sum test, and MMRM in the same manner as described in [Section 8.1](#). The LS means  $\pm$  SE of monthly change from baseline values estimated by the MMRM will also be plotted.

For the endpoint 2), each TEV-48125 group and the placebo group will be compared using Cochran-Mantel-Haenszel (CMH) test stratified by baseline preventive medication use. The difference in the endpoint 2) between each TEV-48125 group and the placebo group and its two-sided 95% confidence interval (a Mantel-Haenszel estimator of the difference and its two-sided 95% confidence interval) will be computed. Additionally, two-sided 95% confidence interval for the endpoint 2) in each treatment group will also be calculated using Clopper-Pearson method. Furthermore, proportion of subjects reaching at least 50% reduction in the monthly number of headache days of at least moderate severity during the 4-week period after each dose (ie, for Month 1, Month 2,

and Month 3) will also be computed in the same manner. Missing data of evaluation will not be imputed.

For the endpoint 5), the HIT-6 total score will be used for disability score. The ANCOVA model and Wilcoxon rank-sum test will be performed as described in [Section 8.1](#).

Frequency distributions will be provided by grade in each time point for each item of HIT-6.

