## **8.3 Exploratory Endpoints**

### **8.3.1 Number of Headache Days of at Least Moderate Severity**

The exploratory endpoints for number of headache days of at least moderate severity in this trial are as follows:

- 1) Mean change from baseline in the weekly number of headache days of at least moderate severity during the 4-week period after the first dose of IMP
- 2) Proportion of subjects reaching at least 75% reduction and total (100%) reduction in the monthly average number of headache days of at least moderate severity during the 12-week period after the first dose of IMP
- 3) Proportion of subjects reaching at least 50% reduction and at least 75% reduction in the number of headache days of at least moderate severity during the 4-week period after the first dose of IMP for whom this level of effect is sustained throughout the 12-week period after the first dose of IMP
- 4) Mean change from baseline in the monthly average number of headache days of at least moderate severity during the 12-week period after the first dose of IMP in subjects receiving concomitant preventive migraine medications
- 5) Mean change from baseline in the number of headache days of at least moderate severity during the 4-week period after the first dose of IMP

For the endpoint 1), similar to the supplementary analysis for the primary endpoint described in [Section 8.1.3](#), an ANCOVA model, Wilcoxon rank-sum test, and MMRM will be used to estimate the mean change from baseline by week (ie, for Week 1, Week 2, Week 3 and Week 4) after the first dose of IMP.

The endpoint 2) will be analyzed using CMH method as described in [Section 8.2.1](#) “endpoint 2)”.

The endpoint 3) will be analyzed using CMH test stratified by baseline preventive migraine medication use similar to “endpoint 2)” in [Section 8.2.1](#). If the subject shows 50% reduction or more at Month 1, Month 2, and also Month3, the level of effect is considered to be sustained throughout the 12-week period after the first dose of IMP for this subject. A subjects with a missing will be treated as a non-responder. Similar definition will be applied to calculate the proportion of sustained responders reaching at least 75% reduction.

The endpoint 4) will be analyzed using an ANCOVA model, Wilcoxon rank-sum test, and MMRM in the same manner as described in [Section 8.1](#).

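### In the sustained-responder analyses a missing month counts as failure only inside the FAS, so dosed subjects with fewer than 10 post-dose diary days leave the denominator

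*SAP*

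**What the plan says.** - **Analysis set.** SAP 5.1 defines the FAS as "Subjects in the SS who have at least 10 days of baseline and post baseline efficacy assessment data" on the primary variable. SAP 8 states: "The FAS will be used for all efficacy analyses".
- **12-week value.** SAP 8.1.4 derives it, prorated to 28 days, only with 10 or more "days of electronic headache diary data after the first dose of IMP".
- **Monthly value.** The same section says that with fewer than 10 "days of electronic headache diary entries for a month, that month's value will be considered as missing".
- **Sustained responders (8.3.1 endpoint 3; 8.3.2 endpoint 3 by reference).** The subject must reach the threshold in each of Months 1, 2 and 3, and "A subjects with a missing will be treated as a non-responder".
- **50% responders (8.2.1 endpoint 2, 12-week and monthly).** "Missing data of evaluation will not be imputed". The 75% and 100% versions, and those for migraine days, follow the same method.
- **Multiple imputation (8.1.2.2).** It covers the primary endpoint only, and applies when the 12-week average "is not missing, but any of the monthly number of headache days of at least moderate severity" is missing.
- **Sample size (4).** The step from 176 to 180 per group was made "taking into account a small percentage of subjects who may be excluded from the FAS".

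**The concern.** For the sustained endpoints the SAP has chosen a rule: no value, no response. A subject with fewer than 10 post-dose diary days in total has fewer than 10 in every month, so all three months are missing and the rule should score that subject as a failure. FAS membership, which depends on what happens after randomization, removes the subject first. The rule therefore reaches people who leave after about two weeks but not those who leave, or stop using the diary, in the first nine days.

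The sustained-response proportions thus describe only subjects who supplied 10 diary days after dosing. If such losses differ between arms, the groups compared are no longer quite those formed by randomization. No other planned analysis brings these subjects back: the imputation analysis starts from subjects who already have a 12-week value and does not cover responder endpoints.

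**Working it through.** **The plan's own figures.** With a difference of 1.7 days, SD 4.9 and 176 per group, z = 1.7 / (4.9 × √(2/176)) = 3.25. Power is Φ(3.25 − 1.96) = 90.2% by the normal approximation and 90.1% by the noncentral t, so the stated figure of more than 90% reproduces. The allowance for FAS exclusions is (180 − 176)/180 = 4/180 = 2.2% per group. It covers every route out of the FAS: not dosed, too little baseline diary, too little post-dose diary.

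**Reading of the FAS rule.** Section 5.1 does not say outright that 10 days are needed in each period separately. Section 8.1.4 asks for 10 days after the first dose before a 12-week value exists, which supports that reading.

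**Two dosed subjects, both with an adequate baseline.** Assume a baseline of 14 headache days. Subject A stops with 12 post-dose diary days, 2 of them headache days. Subject B has 9 post-dose diary days.

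| Endpoint | A (12 days) | B (9 days) |
|---|---|---|
| In the FAS | yes | no |
| 12-week 50% response | 2/12 × 28 = 4.7; reduction 1 − 4.7/14 = 67%: responder | not counted |
| Month 1 50% response | classed on observed days | not counted |
| Months 2 and 3 50% response | missing, not imputed | not counted |
| Sustained 50% or 75% response | Months 2 and 3 missing: non-responder | not counted |

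Only in the last row does the SAP score missingness as failure on one side of the 10-day line and drop it on the other.

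**Size.** The SAP gives no responder rates, so these are assumptions: FAS rates of 40% or 30% on active and 20% on placebo, with 180 dosed per arm. Let a and b be the numbers excluded on active and placebo. Responders are the FAS rate times (180 − a) or (180 − b), rounded. The FAS analysis divides by 180 − a and 180 − b; non-responder counting divides by 180. The shift is approximately (active rate × a − placebo rate × b)/180.

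| Rates | a, b | FAS difference (points) | All-dosed difference (points) | Shift |
|---|---|---|---|---|
| 40%, 20% | 4, 4 | 70/176 − 35/176 = 19.9 | 70/180 − 35/180 = 19.4 | +0.4 |
| 40%, 20% | 8, 2 | 69/172 − 36/178 = 19.9 | 69/180 − 36/180 = 18.3 | +1.6 |
| 40%, 20% | 2, 8 | 71/178 − 34/172 = 20.1 | 71/180 − 34/180 = 20.6 | −0.4 |
| 30%, 20% | 4, 4 | 53/176 − 35/176 = 10.2 | 53/180 − 35/180 = 10.0 | +0.2 |
| 30%, 20% | 8, 2 | 52/172 − 36/178 = 10.0 | 52/180 − 36/180 = 8.9 | +1.1 |
| 30%, 20% | 2, 8 | 53/178 − 34/172 = 10.0 | 53/180 − 34/180 = 10.6 | −0.5 |

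Shifts use unrounded differences. A wholly one-sided loss of 8 active and 0 placebo gives 69/172 − 36/180 = 20.1 against 69/180 − 36/180 = 18.3, a shift of 1.8 points at 40%/20%. Eight in one arm is 8/180 = 4.4%, twice the planned allowance. By the approximate formula, lower response rates at the same exclusions give proportionally smaller shifts.

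**The case against.** The FAS rule is prespecified, identical in all arms, analysed as randomized, and set at the same 10 days that the 12-week value needs. Section 7.1 already reports FAS exclusions by group, so an imbalance would be visible. The closed testing procedure in 8.1.1 covers only the primary endpoint. All of this stands, and it keeps the point minor.

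A reader might go further and infer that subjects who stop slightly later count as non-responders in every responder analysis, or that the SAP has a general non-responder rule that it breaks. The SAP does not support either. The rule is stated only for endpoint 3 of 8.3.1, with 8.3.2 following by reference. On the 12-week rates a later stopper is prorated and can be a responder, as subject A is, and Section 8.2.1 rules out imputation. Forcing only the under-10-day subjects to failure in the main analysis of those endpoints would create a new break at day 10.

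A reader might also infer that the excluded subjects are early treatment failures, or that excluding them favours active treatment. The criterion is diary days: someone who takes all three doses but makes nine entries is excluded too. Placebo subjects also receive three injections at baseline (3.2), so injection burden gives no ground for presuming an imbalance, and the table shows shifts both ways. What remains is that, for endpoint 3, none of these arguments explains why three missing months should be treated differently from two.

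**Conclusion.** The inconsistency is real and confined to the sustained-responder endpoints. There, a dosed subject with 10 or more post-dose diary days who leaves any month short is a non-responder, while a dosed subject with fewer than 10 is not counted. For the 12-week responder endpoints the same subjects are also left out, but this agrees with the no-imputation rule, so it calls for a sensitivity analysis only.

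The expected effect is small: about 0.2 to 1.6 points on the treatment difference for exclusions of 4:4, 8:2 and 2:8, in either direction. This rests on assumed responder rates and splits, and on all exclusions being for too little post-dose diary. Since the 2.2% allowance also covers undosed subjects and those without an adequate baseline, fewer than 4 per group may be affected. No confirmatory conclusion depends on it.

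**What to change.** 1. **8.3.1 endpoint 3 and 8.3.2 endpoint 3:** use as denominator all randomized and dosed subjects with at least 10 baseline diary days. State that those with fewer than 10 post-dose diary days, for whatever reason, are non-responders under the existing missing-month rule.
2. **8.2.1 endpoint 2, and endpoint 2 of 8.3.1 and 8.3.2:** keep the FAS analysis as main. Add a sensitivity analysis of the 12-week rates in the same dosed set, with these subjects as non-responders.
3. **Section 8:** note the exception to the statement that all efficacy analyses use the FAS. The continuous endpoints stay as they are.

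The cost is SAP wording, a changed denominator and one extra analysis, with no new data. Reported sustained-response rates would be slightly lower.
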